Protocol Title: Short vs Long Dental Implants for the Fixed Rehabilitation of the Fully Edentulous Mandible

CEAOUSUN1327012010

PI: [name], DDS

Version Date: 20/06/2019

NCT03509402

Background, Significance, and Rationale

The clinical use of dental implants in the rehabilitation of totally and partially edentulous patients represents to date a long-term well documented and highly predictable procedure (for review see Cochran 1996, Esposito et al. 1998a, b). Historically, surgeons aimed for placement of the longest possible implants, in order to reach high bone-to-implant contact rates with the machined implants available at that time. The use of modern "rough" implants has been demonstrated to positively correlate with bone-to-implant contact rate and bone anchorage, leading to a significant enlargement of clinical indications for implant-supported rehabilitations (Gotfredsen et al. 1992; Cooper et al. 2000; Ivanoff et al. 2001; Shalabi et al. 2006).

The available amount of bone still remains the main limitation for implant placement. In cases of reduced bone height, standard length fixtures could be inserted only after advanced surgical treatments, such as vertical ridge augmentation, mandibular nerve transposition, and maxillary sinus lift. Patients often refuse such invasive procedures, ending up renouncing implant rehabilitation. For this reason, the possibility of using short implants is particularly fascinating, since it provides reliable solutions also in the numerous cases of reduced bone height, significantly expanding clinical indications for implant treatment. The use of short implants, moreover, presents also "absolute" benefits for patients in terms of limited foreign body, less invasive surgery (less biological tissue replacement), and reduced risk of damaging anatomical structures.

For "short" implants we refer to fixtures with an intraosseous length $\leq 8 \text{ mm}$ (Renouard & Nisand 2006).

Short implants historically have been associated with higher failure rates than longer ones. On the other hand, a number of studies have failed to find differences in the survival rate of short and long implants (for review see Renouard & Nisand 2006, Morand & Irinakis 2007).

The discrepancies between these two groups of studies may relate to different factors such as the implant surface employed, the surgical protocol adopted in relation to the local bone density, the type of edentulism, and the prosthetic technique chosen.

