The secondary outcomes will include: (i) implant survival rate, (ii) prosthesis survival rate, (iii) biological or technical complications. Surviving implant or prosthesis will be considered those still in function at the follow-up. Biological complications included peri-implant mucositis, defined as a reversible inflammation of the soft tissues surrounding an implant in function with no loss of supporting bone, and peri-implantitis, defined as an inflammatory process affecting the tissues around an osseointegrated implant in function resulting in loss of supporting bone (Zitzmann & Berglundh 2008. Technical complications will be categorized in minor and major complications. The formers require only chair side repair and included screw loosening, and veneer material fracture. The latter require additional laboratory procedures and/or replacement components and included prosthesis or framework fracture, screw fracture, implant fracture, extended wear requiring veneer renewal.

Sample size calculation

Sample size calculation revealed that group sample sizes of 13 per group achieved 80% power to detect noninferiority using a two-sample, one-sided test. The margin of non-inferiority (δ), that is the threshold value judged as clinically relevant, was 1.0 mm. The true difference between the means was assumed to be 0.0. In consideration of the one-tail nature of the non-inferiority test, the significance level (alpha) was set at 0.025. The data were drawn from populations with standard deviations of 0.9 and 0.9. Such a value was based on the long-term marginal bone loss data from the population of mandibular edentulous patients rehabilitated with Toronto bridges supported by conventionally loaded inter-foraminal long implants (Ekelund, Lindquist, Carlsson, & Jemt, 2003). Fifteen patients per group will be recruited to compensate for possible drop-outs.

Patient enrollment

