Peri-apical radiographs will be taken with Rinn Universal Collimator (Dentsply RINN, York, PA, USA) to limit exposure levels and Rinn film holders (XPC Extension Cone Paralleling System, Dentsply RINN, York, PA, USA), for correct positioning. Film-holder's position will be noted down for each implant site to increase reproducibility. The MBL will be determined (ImageJ 1.48a, National Institutes of Health, Bethesda, MD, USA) as the distance between the top of the micro-thread implant region and the most coronal level of the boneto-implant contact, using inter-thread distance for calibration. All the radiographic measurements will be performed by an experienced examiner not otherwise involved in the study, who will be kept unaware of the implant length by duly masking the radiograms. Mesial and distal MBL will be measured at each fixture and the MBLc from the baseline will be calculated at each follow-up (negative values in case of bone loss). Mean values will be calculated at the implant, patient and group level.

Statistical analysis plan

Descriptive statistics (means, standard deviations) of continuous variables and relative frequencies of discrete variables will be computed for each group separately using a statistical software program. Data will be analysed by an examiner blinded to the experimental groups using the patient as the statistical unit unless differently specified. Intention-to-treat (ITT) analysis will be adopted. The Fisher exact test for discrete intergroup variables and the one-sided Mann-Whitney U-test for MBLc values will be applied, because of the nature of the data. For primary outcome, statistical significance will be set at the alpha level of 0.025 using a one-sided test, while for two-sided tests statistical significance will be set at the alpha level of 0.05.

References

Bryant SR, MacDonald-Jankowski D & Kim K. (2007) Does the type of implant prosthesis affect outcomes for the completely edentulous arch? International Journal of Oral and Maxillofacial Implants 22 Suppl, 117-39.

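### Survival and complications are judged by Fisher's exact test alone, with no interval: valid, but conservative at 13 to 15 patients per arm (minor; secondary outcomes only)

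*Combined protocol and SAP*

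**What the plan says.** The section on primary and secondary outcomes lists the outcomes at issue: "The secondary outcomes will include: (i) implant survival rate, (ii) prosthesis survival rate, (iii) biological or technical complications". The Statistical analysis plan section assigns "The Fisher exact test for discrete intergroup variables" and analyses the data "using the patient as the statistical unit unless differently specified", under intention to treat.

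On significance levels, that section gives MBLc a one-sided test at 0.025. A separate clause covers the rest: "while for two-sided tests statistical significance will be set at the alpha level of 0.05". It does not say in so many words that the Fisher tests are two-sided. I infer it, because the only one-sided test named is the one for MBLc.

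On numbers, the sample size section says "Fifteen patients per group will be recruited to compensate for possible drop-outs".

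For the discrete outcomes the planned output is relative frequencies and a p-value. No interval, margin, detectable difference or power is given for them.

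**The concern.** Fisher's test conditions on the total number of events. With about 15 patients per arm few p-values are possible, so the chance of crossing 0.05 under equal rates lies well below 5%, and power falls with it.

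This matters because the background section states: "Short implants historically have been associated with higher failure rates than longer ones". Failures are therefore what a reader will look for beside the bone-level result. If the only output is a p-value from a conservative test, a non-significant result says very little about whether short implants fail more often. Nothing in the planned output shows how large a difference has been left open.

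**Working it through.** **Inputs.** From the plan: 15 recruited per arm, 13 per arm calculated, patient as unit, Fisher's test, threshold 0.05. Assumed: two-sided testing; each outcome reduced to yes/no per patient; all event rates, since the plan gives none.

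**The plan's own figure.** The only stated sample size is for the primary outcome: n = 2(1.96 + 0.84)² × 0.9² / 1.0² = 2 × 7.85 × 0.81 = 12.7, so 13 per arm. This reproduces under the normal approximation. There is no stated figure for the Fisher tests.

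**Step 1: which splits are significant at 15 vs 15.** For k events vs 0, two-sided p = 2·C(15,k)/C(30,k).
- k = 3: p = 0.224
- k = 4: 2 × 1365/27405 = 0.0996
- k = 5: 2 × 3003/142506 = 0.042

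So 5 vs 0 is needed; against 1 event, 7 are needed. A 4 vs 0 split gives p = 0.098 at 14 vs 14 and 0.096 at 13 vs 13.

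**Step 2: true type I error.** Sum the binomial probabilities of all tables with p ≤ 0.05 under a common event rate, then maximise over that rate.
- Fisher: 1.77% (15 vs 15), 2.1% (14 vs 14), 2.9% (13 vs 13). At 15 vs 15 it is 0.06% if the common rate is 5%, and 0.55% if it is 10%.
- Boschloo (tables ordered by Fisher's p, maximised over the common rate): 4.33%, 4.16% and 4.85%. For 4/15 vs 0/15 its p is 0.043.

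**Step 3: power at 15 vs 15.** If one arm's true rate is 0%, power is P(X ≥ 5) for Fisher and P(X ≥ 4) for Boschloo, with X ~ Binomial(15, rate). The other rows sum over both binomials.

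| True rates (assumed) | Fisher | Boschloo |
|---|---|---|
| 0% vs 10% | 1.3% | 5.6% |
| 5% vs 15% | 3.0% | 8.9% |
| 0% vs 20% | 16% | 35% |
| 5% vs 25% | 17% | 31% |
| 0% vs 30% | 48% | 70% |
| 10% vs 40% | 33% | 46% |

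**Step 4: unequal arms.** At 15 vs 14 the result depends on which arm is short.
- 4/14 vs 0/15: Fisher p = C(14,4)/C(29,4) = 1001/23751 = 0.042, already significant. The opposite extreme has probability 1365/23751 = 0.057, which is larger, so it is not added.
- 4/15 vs 0/14: Fisher p = (1365 + 1001)/23751 = 0.0996 and Boschloo p = 0.067. Both miss.
- Power, Fisher then Boschloo, events in the smaller arm: 30.2% and 30.2% at 0% vs 20%; 64.5% and 64.5% at 0% vs 30%; 40.5% and 45.9% at 10% vs 40%.
- Events in the larger arm: 16.4% and 16.4%; 48.5% and 48.5%; 34.7% and 38.4%.

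At 15 vs 13 and 14 vs 13 the gain is 0 to 3 points.

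**Step 5: what an interval would show.** Newcombe's score-based 95% intervals for the risk difference, in percentage points:
- 3/15 vs 0/15: −4 to +45 (Fisher p = 0.22)
- 4/15 vs 0/15: +1 to +52 (Fisher p = 0.0996)
- 0/15 vs 0/15: −20 to +20

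**The case against.** The strongest reply is that nothing here is a mistake. Fisher's test is a standard choice for small samples and keeps the type I error at or below 0.05. The 0.05 in the plan is a significance threshold, not a promise about attained size. Every exact test on discrete data falls short of nominal, including Boschloo's (0.5% at a common rate of 5%, 15 vs 15). All of this stands, so a reader who infers from the 1.8% ceiling that the plan misstates its error rate goes too far.

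The second reply is that the benefit of changing the test is fragile. The plan expects drop-outs and gives no rule for missing patients under intention to treat, so unequal arms are plausible over five years. One unbalanced loss removes most or all of the gain. It also breaks any general statement that 4 vs 0 is non-significant, since 4/14 vs 0/15 reaches p = 0.042. This stands too. The gain remains if all 30 patients are analysed or losses are balanced.

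Third, the plan calls this type of rehabilitation highly predictable. If failures are rare, sample size limits the comparison far more than the choice of test, as the 0% vs 10% row shows. That is correct, and it strengthens the case for an interval.

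Finally, a reader might infer that the plan treats p>0.05 on survival as equivalence and so favours the short implant. The documents do not support this: the null hypothesis and the 1.0 mm margin concern MBLc only, and no similarity claim is attached to the secondary outcomes. The risk lies in later interpretation, which the plan does nothing to guard against.

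**Conclusion.** The point holds as a minor one. It concerns lost power and missing estimation on secondary outcomes; the test itself is not in error and the primary analysis is untouched.

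The more important gap is the absent interval. Even no events in either arm would leave differences of up to 20 points open, and the planned output would not show it. The choice of test comes second. Boschloo's gain is large with equal arms (19 points at 0% vs 20% and 22 points at 0% vs 30%, 15 vs 15), about 0 to 5 points at 15 vs 14, 15 vs 13 or 14 vs 13, and small in absolute terms for rare events whatever the arms.

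These figures rest on two-sided testing (inferred), the patient as unit, and assumed event rates. If implants were tested one by one (75 vs 75), Fisher's ceiling would be about 4.1%, but that ignores clustering within patients and departs from the plan's default unit.

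**What to change.** In the Statistical analysis plan section:

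1. For each patient-level binary secondary outcome, report the risk difference (short minus long) with a 95% score-based or exact interval, naming the method in advance. For implant survival, define the patient-level variable, for example at least one implant lost.
2. State that the secondary conclusion is read from the interval, and that p>0.05 is not evidence of similar survival or complication rates.
3. State that these tests are two-sided at 0.05, and replace Fisher's test with Boschloo's exact unconditional test. It holds the level and rejects whenever Fisher's does. Specify it before unblinding, since a switch made after seeing p = 0.10 would not be credible.
4. State that the gain is large only with equal arms and that power for rare events stays very low under either test.

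Items 1 and 2 stand even if the sponsor keeps Fisher's test. The cost is SAP wording and a standard software routine, with no new patients, visits or data. The one drawback is that Boschloo's test is less familiar to dental readers.

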After 3 months of healing all implants will be exposed by separated linear incisions, cover screws will be removed and replaced by healing abutments. After 1 week, the final abutment (Uni-abutment, Astra Tech Implant System, Dentsply Sirona Implants, Mölndal, Sweden) will be screwed on each implant and an abutment-level impression will be registered. Expert clinicians will follow all the prosthetic phases. All patients will receive a fixed screw-retained full-arch prosthesis with distal cantilevers. The length of the bridge cantilevers will be calculated to minimize implant overloading (Mericske-Stern, Taylor & Belser, 2000). All prosthetic procedures will be made according to the Astra Tech Implant System procedures and products manuals.

Supportive peri-implant therapy

Patients will be instructed in proper hygiene measures, suitably designed and based on their individual needs, including tooth brushing, interdental brushing, flossing, and rinsing with an antiseptic mouth. Patients will be recalled every six months for a control visit and professional supragingival ultrasonic debridement and polishing.

Baseline and follow-up examinations

Radiographs and clinical examinations will be performed, together with primary and secondary outcome assessment, at baseline (final restoration placement), and after 1, 3 and 5 years of loading.

Clinical examination will include visual inspection to detect signs of inflammation as well as the occurrence of technical complications. Peri-implant probing depth, the presence of visible plaque and bleeding/suppuration on probing around implants will be also evaluated.

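### Five-year implant and prosthesis survival is compared only as a yes/no status with Fisher's exact test, with no time-to-event method and no rule for scoring drop-outs

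*Combined protocol and SAP*

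**What the plan says.** The section on primary and secondary outcomes lists the secondary outcomes as "i) implant survival rate, (ii) prosthesis survival rate, (iii) biological or technical complications". It defines survival by status alone: "Surviving implant or prosthesis will be considered those still in function at the follow-up". Outcomes are assessed "at baseline (final restoration placement), and after 1, 3 and 5 years of loading" (Baseline and follow-up examinations). Between those visits, "Patients will be recalled every six months for a control visit" (Supportive peri-implant therapy).

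The sample size section expects attrition: "Fifteen patients per group will be recruited to compensate for possible drop-outs", against 13 required.

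The statistical analysis plan gives relative frequencies for discrete variables and one test for them: "The Fisher exact test for discrete intergroup variables". The analysis is to be made "using the patient as the statistical unit unless differently specified", and "Intention-to-treat (ITT) analysis will be adopted". Nowhere is there a time-to-event method, a time origin, a denominator for the survival rates, or a rule for a patient whose status at a visit is unknown.

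**The concern.** Loss of an implant or a bridge can happen at any time over five years, and some patients will be followed for only part of that period. A Fisher table has no cell for a patient known to be event-free at year 3 and not seen afterwards. That patient must be left out, assumed a success or assumed a failure. For a patient who lost an implant at year 1 and then left, the plan does not say whether the known failure stands in the year-5 table.

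The choice matters because leaving after a failure is a plausible form of drop-out, and it would be commoner in whichever arm fails more. The background section describes the debate over short implants in terms of failure and survival rates, so readers will look at these figures. As written, one dataset supports several survival rates, and the choice between them would be made after the data are seen.

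**Working it through.** **Drop-out allowance.** The plan's sample size reproduces: n = 2 × [0.9 × (1.960 + 0.842)]² / 1.0² = 12.7, rounded up to 13 per group. Recruiting 15 allows 2/15 = 13.3% drop-out. That calculation concerns marginal bone level; no failure rate or power is stated for survival. It is used here only for the allowance of two drop-outs.

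**One arm of 15, two drop-outs, no failures among the 13 completers.** Let f be the number of drop-outs who lost one implant before leaving. Each patient has five implants (First surgical phase), 75 in all.

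| Scoring rule | Patient level | Implant level |
|---|---|---|
| Completers only, any f | 13/13 = 100% | 65/65 = 100% |
| Observed losses kept, all 15 counted, f = 1 | 14/15 = 93.3% | 74/75 = 98.7% |
| Observed losses kept, all 15 counted, f = 2 | 13/15 = 86.7% | 73/75 = 97.3% |
| Absent counted as not surviving, any f | 13/15 = 86.7% | 65/75 = 86.7% |

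The first rule overstates patient-level survival by 6.7 points (f = 1) or 13.3 points (f = 2). The last understates it by 13.3 points when f = 0.

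**Completers only, in general.** With true failure p, drop-out q after failure and 10% drop-out otherwise, the observed failure rate is p(1 − q) / [p(1 − q) + 0.9(1 − p)]. For p = 0.20:

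- q = 0.3: 0.14 / (0.14 + 0.72) = 16.3%
- q = 0.5: 0.10 / (0.10 + 0.72) = 12.2%
- q = 0.1: 0.18 / (0.18 + 0.72) = 20.0%, so bias needs drop-out that differs by failure.

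**Comparing estimators by simulation.** Assumptions: 15 per arm, losses found equally at years 1, 3 and 5, true failure 20%, 30% leaving after a loss found at year 1 or 3, and 10% drop-out otherwise. Mean estimated failure was:

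- completers only: 17.0%
- all 15, with event-free leavers counted as successes: 18.8%
- observed losses kept, event-free leavers excluded: 20.6%
- Kaplan-Meier: 20.0%

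**Comparing tests.** Same set-up, two-sided 0.05, assumed failure 40% v 5%:

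| Leaving after an early loss | Fisher, completers only | Fisher, observed losses kept, event-free leavers excluded | Permutation log-rank |
|---|---|---|---|
| 30% | 44% | 54% | 59% |
| 50% | 35% | 55% | 59% |

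Keeping observed losses adds 54 − 44 = 10 and 55 − 35 = 20 points. The log-rank test adds a further 59 − 54 = 5 and 59 − 55 = 4. These figures move by two or three points between runs. The log-rank error rate stayed below 4% in the null settings. At 20% v 5% with 30% leaving, power is about 7%, 11% and 13%.

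**Effect on the p-value.** Fully counted, 2/15 v 0/15 gives Fisher p = 2 × 105/435 = 0.48. Significance needs 5/15 v 0/15: p = 2 × 3,003/142,506 = 0.042.

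**The case against.** A reader might infer that a patient who loses an implant and then leaves necessarily vanishes from the five-year comparison, so that survival is overstated. The documents do not say that. No sentence removes such a patient; a lost implant can never meet the definition of being in function; a loss found at year 1 or 3 also enters that visit's rate; and the intention-to-treat statement points towards keeping randomised patients. Read literally, the definition could count event-free leavers as failures, which would understate survival. This objection stands: the direction of error is open. It does not remove the problem, because intention-to-treat settles the arm in which a patient is analysed and not how an unobserved status is scored.

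A second objection is that Fisher's test is not the main culprit, since it can be run on whether a patient ever failed. This also largely stands: most of the power gain comes from that step alone. What remains is that event-free leavers must still be excluded or guessed. In the 20% failure setting, guessing success gave 18.8% and excluding gave 20.6%, while Kaplan-Meier gave 20.0%.

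Third, the failure and drop-out rates in the simulations are assumptions, and 40% v 5% is extreme for a rehabilitation that the protocol describes as highly predictable. At 10% v 5%, every method has power of about 2% or less. The case for change therefore rests on the reported rates and not on power.

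**Conclusion.** The point holds as a gap with a cheap, better alternative. Survival over five years is scored as status at a visit and tested only with Fisher's exact test; drop-outs are expected, and nothing says how they are scored. Within the plan's own allowance of two drop-outs per arm, the patient-level rate can be overstated or understated by up to 13.3 points. Each extreme is a worst case: the first needs both drop-outs to have failed before leaving, the second needs neither to have failed.

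The documents do not support the stronger claims that failures are bound to be lost from the comparison, or that Fisher's test itself is what loses them. The log-rank test's own contribution is about 4 to 5 points of power, in a scenario with assumed rates. Kaplan-Meier's advantage also assumes that patients who leave event-free carry the same later risk as those who stay. The outcome is secondary and unpowered, so the change should be made but does not bear on the primary conclusion.

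**What to change.** In the statistical analysis plan:

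- Define patient-level time to first implant loss, counted from implant placement so that losses before loading are included, and time to prosthesis loss, counted from prosthesis installation.
- State that an observed loss remains a failure whatever happens later, and that patients who leave event-free are censored at their last visit.
- Report Kaplan-Meier survival at 1, 3 and 5 years by arm with confidence intervals, saying from which origin the years are counted.
- Add an implant-level survival rate with an interval that allows for five implants per patient.
- Compare arms with a permutation log-rank test at two-sided 0.05, in place of Fisher's test on five-year status. Permutation is needed because the large-sample version is unreliable at 15 per arm.

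If only one sentence can be added, the rule that observed losses are kept matters most.

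The cost is SAP wording, plus a check that the date of each loss and of last contact is recorded. The documents do not say so, though the scheduled visits and six-monthly recalls should supply both. With few events the intervals will be wide.

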Well-designed randomized controlled clinical trials demonstrating the efficacy of short implant rehabilitations are lacking to date.

The clinical performance of short and long implants should be compared at the level of areas having a good and comparable bone quality, the same bone height (this assumes the installation of short implants in sites able to receive longer ones), and for the resolution of the same type of edentulism by means of an identical prosthetic solution.

A reliable option is represented by 5 implants positioned in the interforaminal region of edentulous mandibles having bone height sufficient to receive standard-length implants, supporting a fixed full-arch prosthesis. The anterior mandibular region is usually characterized by high bone quality. Furthermore, the above-mentioned type of full-arch implant-supported rehabilitation possesses the best evidence of long-term success (Ekelund et al. 2003; Bryant et al 2007), being historically the first one performed and, to date, the most predictable too.

Specific Aims and Hypotheses

The aim of the present study is to evaluate the efficacy of 6 mm short implants compared with 11 mm long implants in comparable anatomic, surgical (no need for bone augmentation procedures), and prosthetic (fixed full-arch mandibular prosthesis) conditions. In particular, the null hypothesis is that there is no difference in terms of marginal bone level change (MBLc) between short and longer implants from prosthetic installation to 5 years of follow-up.

Study design and general information

This study has been designed as a multicenter parallel-group randomized controlled clinical trial (RCT) with a 1:1 allocation ratio. Three italian centers will be involved to the study. It will be reported according to the

CONSORT statement (http://www.consort-statement.org/). The Declaration of Helsinki principles will be followed, and all patients will sign a written informed consent form. The research protocol has been approved by the ethical committee of the University of Campania "Luigi Vanvitelli" (Aut. N. 13/2010).

Primary and secondary outcomes

The primary outcome will be the radiographic MBLc expressed as the change of MBL from prosthetic installation to the follow-up.

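### The trial is sized for non-inferiority with a 1.0 mm margin, but the stated null is no difference and the SAP's primary test has no margin and no direction

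*Combined protocol and SAP*

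**What the plan says.** Three sections bear on the primary comparison.

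- **Sample size calculation.** The trial is sized for non-inferiority: "group sample sizes of 13 per group achieved 80% power to detect noninferiority using a two-sample, one-sided test". The margin is explicit: "The margin of non-inferiority (δ), that is the threshold value judged as clinically relevant, was 1.0 mm". So is the reason for the alpha level: "In consideration of the one-tail nature of the non-inferiority test, the significance level (alpha) was set at 0.025". The true difference is taken as 0 and the SD as 0.9 mm in both groups. On attrition: "Fifteen patients per group will be recruited to compensate for possible drop-outs".
- **Specific Aims and Hypotheses.** The only hypothesis stated is that "the null hypothesis is that there is no difference in terms of marginal bone level change (MBLc) between short and longer implants", over the period from prosthesis installation to 5 years.
- **Statistical analysis plan.** For the primary outcome, "the one-sided Mann-Whitney U-test for MBLc values will be applied, because of the nature of the data". On the level: "For primary outcome, statistical significance will be set at the alpha level of 0.025 using a one-sided test".

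The follow-up section defines MBLc so that bone loss is negative. The margin appears only in the sample size section.

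**The concern.** A Mann-Whitney test on MBLc values compares the groups at zero difference unless one arm is shifted by the margin. The SAP gives no shift, no confidence limit to set against 1.0 mm, and no tail. The null in the Aims is also zero difference. An analyst who follows the text therefore runs a test other than the one the sample size assumes, and no sentence says which result would show that 6 mm implants are non-inferior.

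Three readings are possible, and they can disagree on the same data:

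- a zero-difference test for short implants being better;
- a zero-difference test for short implants being worse, with non-significance taken as reassurance;
- a test against the 1.0 mm margin.

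The first is valid but answers a superiority question. The second does not control the error rate at the margin. Only the third matches the design. The plan does not choose among them, so the choice could be made after the data are seen, and it decides the trial's main conclusion.

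**Working it through.** **Inputs from the sample size section:** margin 1.0 mm; SD 0.9 mm in each group; true difference 0; one-sided alpha 0.025; power 80%; 13 per group, 15 recruited.

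**1. The plan's own figure.** With the normal approximation,

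n per group = 2 × [SD × (z₀.₉₇₅ + z₀.₈₀) / margin]² = 2 × [0.9 × (1.960 + 0.842) / 1.0]² = 12.72, rounded up to 13.

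The stated 13 is reproduced. Power at 13 per group is 80.9% by the normal approximation and 77.6% by the noncentral t. A two-sided 0.05 superiority test for a 1.0 mm difference also gives 13, so the sample size alone does not show which hypothesis is to be tested.

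**2. The test named in the SAP.** Exact one-sided Mann-Whitney test at 0.025, 200,000 simulated trials per cell, SD 0.9 mm. Data are normal except in the rows marked skewed, which use a gamma distribution with shape 2 and the same SD. That shape is an assumption; the documents do not supply one.

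| | 13 per arm | 14 per arm | 15 per arm |
|---|---|---|---|
| Critical value of U | 124 | 141 | 161 |
| Exact size | 2.21% | 2.49% | 2.27% |
| No shift, short better: success at true difference 0 | 2.2% | – | 2.3% |
| No shift, short worse: non-significant when short is worse by 1.0 mm | 26.5% | 21.5% | 19.8% |
| Same, skewed | 16.7% | – | 11.2% |
| 1.0 mm shift: power at true difference 0 | 73.3% | 78.7% | 80.4% |
| Same, skewed | 83.1% | – | 88.8% |
| 1.0 mm shift: type I error when short is worse by 1.0 mm | 2.2% | 2.5% | 2.2% |

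A separate run with 40,000 normal-data trials per cell at 13 and 15 per arm agreed to within about half a percentage point (for example, 26.7% and 19.4% in the non-significance row).

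**3. Reading the table.**

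- *No shift, short better.* At true difference 0 the tested null is true, so the rejection rate is simply the size of the test. The 80% planned in the sample size section belongs to a different hypothesis.
- *No shift, short worse, non-significance read as success.* The false-pass rate at the margin is one minus the power of a zero-difference test. At 15 per arm with normal data: 1 − 0.802 = 0.198. The design's limit is 0.025.
- *Shift of 1.0 mm.* The error rate at the margin holds, and power is near the planned value. This is the only version consistent with the sample size section.

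**The case against.** The strongest reply is that the intention can be recovered. Protocol and SAP are one short document. The sample size section names a non-inferiority test, gives the margin and explains the one-sided 0.025 level. The SAP repeats that level for the primary outcome and keeps 0.05 for two-sided tests. The surgical section makes 6 mm the test arm and 11 mm the control, and bone loss is negative, so the direction can be worked out. On this view the gap is only how the margin enters the rank test, plus a loosely worded null. The reply adds that the 2.2–2.3% figure is a test size and not lost power, that the 20–27% figure depends on a rule found nowhere in the plan, and that the power cost depends on the normal model.

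Much of this stands. Non-inferiority was probably intended. The 2.2–2.3% shows that the question differs and does not measure damage. The 20–27% is a risk scenario only. With skewed data the shifted test exceeds 80% power even at 13 per arm.

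The reply does not remove the problem. Inferring a margin-based test means setting aside the one null that is written and adding a step the SAP does not mention. Matching alpha levels do not put 1.0 mm into a rank test.

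**Conclusion.** The concern holds. As written, the primary analysis is a zero-difference test with no stated tail, while the trial is sized for non-inferiority at 1.0 mm. The sample size arithmetic itself is sound. This must be fixed, because it governs the primary conclusion.

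Testing for short implants being better, against zero, would succeed about 2% of the time under the planning assumption of no true difference. If non-significance for short implants being worse were taken as non-inferiority, implants worse by the full margin would pass 20% (15 per arm) to 26–27% (13 per arm) of the time with normal data, or 11% to 17% with the skewed data, against 2.5%.

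The figures assume the plan's SD of 0.9 mm, patient-level values, a pure location shift between arms, and the stated number analysed in each arm. The second set is conditional on a reading that the plan does not adopt.

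**What to change.** - **Aims.** Replace the no-difference null with H0: short minus long 5-year patient-level MBLc ≤ −1.0 mm, against H1: > −1.0 mm, with bone loss negative. The 5-year point comes from the Aims. The outcome definition does not name a visit, and examinations are planned at 1, 3 and 5 years, so it should be aligned.
- **SAP.** Add 1.0 mm to each short-implant patient's MBLc, then apply the one-sided 0.025 Mann-Whitney test. Equivalently, require the lower limit of the two-sided 95% Hodges-Lehmann interval for short minus long to exceed −1.0 mm. State the location-shift assumption that both forms need.
- **Interpretation.** State that a non-significant zero-difference test will not be read as non-inferiority.
- **Sample size.** Qualify the 80% power statement for the rank test. With normal data it is about 80% at 15 per arm, 79% at 14 and 73% at 13, so under that model the two extra patients per arm meant for drop-outs are needed to reach 80%. With the skewed data it is 83% at 13.

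The cost is wording in three sections. Margin, alpha, test and recruitment target stay as they are, and no new data are needed. The documents do not say whether outcome data existed at the version date of 20/06/2019; if they did, the change should be a dated and disclosed amendment.
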